Effect of Iosartan on Mucociliary dysfunction in patients with Chronic Obstructive Pulmonary Disease (COPD) and Chronic Bronchitis

PROTOCOL

VERSION 5.0 DATE: February 1, 2019 NCT Number: NCT02416102

Principal Investigator:	[name] [name] Division of Pulmonary, Allergy, Critical Care, and Sleep Medicine University of Miami School Of Medicine [name] Office: [contact]

Sponsor:

[name] [name] Division of Pulmonary, Allergy, Critical Care, and Sleep Medicine University of Miami School Of Medicine [name] Office: [contact]

Funding:

Flight Attendant Medical Research Institute

Objectives

On this study we will test the hypothesis that inhibiting TGF-ß signaling with losartan in smokers and ex-smokers with chronic obstructive pulmonary disease (COPD) leads to increased Cl⁻ conductance through CaCC in vivo by assessing nasal potential difference (NPD), a surrogate for potential differences in epithelia of the lower airways and therefore an appropriate outcome variable for a proof of concept clinical trial, avoiding the long trial durations typical for COPD studies. NPD measurements will be done in the untreated cohort and repeated while giving 50 mg and subsequently 100 mg losartan for 4 weeks each. The study design will allow intra-individual comparisons of the effects of losartan on BK channel function as measured by Cl⁻ conductance through CaCC.

Background

Mucociliary clearance (MCC), a major airway host defense system, is dysfunctional in patients with smoking-associated lung diseases such as chronic bronchitis and COPD. Mucociliary dysfunction accounts for the clinical hallmarks of these diseases, namely chronic productive cough and recurrent respiratory infections. For appropriate MCC, motile cilia beat in a highly regulated airway surface liquid (ASL) that optimizes ciliary beat frequency (CBF) and efficiency and provides hydration to mucus. Airway epithelia use ion transport (absorption of Na⁺ and secretion of K⁺ and Cl⁻) to regulate ASL volume and composition to optimize MCC.

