We recently found that ATP-dependent, apical Cl⁻ secretion and ASL fluid regulation depend on the activation of apically expressed large conductance, Ca²⁺ activated and voltage-dependent potassium (BK) channels. By secreting K⁺, apical BK channels provide a driving force for apical Cl⁻ secretion via Cl⁻ channels, forming a so-called apical loop current. This BK function is critically important since inhibition of BK channels reduces ASL volume significantly (in the presence or absence of functional CFTR), thus shifting the focus of ASL volume regulation upstream from Cl⁻ channels to BK channels.

Increased airway TGF-ß1 expression and signaling is common in active cigarette smokers and ex-smokers with COPD. Our preliminary data show that TGF-ß1 and cigarette smoke exposure decrease BK activity and cause ASL volume depletion. We therefore propose that smoke exposure, via TGF-ß1 production, leads to apical BK channel dysfunction to cause ASL volume depletion and mucociliary dysfunction in smokers and ex-smokers with COPD. BK rescue is associated with increased ASL volume and CBF. Therefore, restoring ASL volume requires BK channel rescue or inhibition of TGF-ß signaling. Clinically used Angiotensin II Receptor Blockers (ARBs) are known to inhibit TGF-ß signaling and present a "low-hanging-fruit" approach (medication already in clinical use) for intervention in COPD. In a murine model, losartan has previously been shown to attenuate cigarette smoke-induced lung injury and to rescue lung architecture. Our preliminary data suggest that losartan partially rescues BK channel function leading to increased ASL volume and CBF in airway epithelial cells exposed to smoke. The long-term goal of this study is therefore to evaluate the effect of currently available and clinically useful TGF-ß1 signaling inhibitors on mucociliary function in individuals with smoke-associated airway diseases, such as chronic bronchitis and COPD.

This is a proof of concept, open label protocol to evaluate the effect of ARB on cigarette smoke-induced lung injury in smokers, ex-smokers with and without COPD, giving 50 mg and subsequently 100 mg losartan for 4 weeks

Study Population

Group I, COPD:

10 ex-smokers not treated with ARBs **with** evidence of fixed airflow obstruction by pulmonary function testing (PFT), decreased DLco **and** with the clinical diagnosis of chronic bronchitis.

Group II, non-COPD:

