- Acute pulmonary exacerbation within 6 weeks from the Screening Visit.
- Subjects with no airflow obstruction by spirometry but with a decrease in DLco < 70% possibly indicating emphysema.
- Significant exposure to environmental tobacco smoke or atmospheric or occupational pollutants for the non-smokers group.
- Urine pregnancy positive test at the Screening Visit.

Treatment arms

Patients will be given four weeks of 50 mg of losartan daily and consequently an additional four weeks of 100 mg of losartan (divided in two doses of 50 mg twice daily). This higher losartan dose was used safely in other clinical trials (www.clinicaltrials.gov; search: losartan and COPD). At the end of each four-week period, participants will be re-evaluated. We will compare treatments using baseline measurements of each individual as his/her own control.

Study Drug:

Cozaar[®], the commercial form of losartan will be obtained from the UMHC Pharmacy and given to the subjects by the PI or study coordinators free of charges. FDA has granted IND exemption for this study. Study drug will be stored as per package instructions in a locked cabined on the research room at UMH 6th floor west room 607. Only the study team has access to this room. The storage area at the study center will be monitored by the staff for temperature consistency with the acceptable storage conditions.

The Investigator is responsible for maintaining accurate study drug accountability records throughout the study.

Each dispensing of study drug will be documented in the subject's study records and in the drug accountability log. Subjects will return all unused study drug for drug accountability. Study drug will be destroyed at the clinical site as per the Institution regulations.

Study Procedures

Once informed consent is signed, the subjects will have an initial visit during which they will have a physical exam (including vital signs), complete study questionnaires and PFTs. All study subjects will undergo the following procedures during a single visit:

History and physical examination will be performed including vital signs and body mass index (BMI) will be recorded.

Laboratory Samples: Urine will be collected for a pregnancy test if applicable and blood test for CMP and CRP will be drawn, if results are not available within 6 months of the Screening visit.

Urine cotinine levels will be measured at the time of study visits to assess smoking status (active or not).

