NPD measurement will be performed according to standard procedures. In this aim, we will use one side of the nose for the evaluation of the function of CFTR and CaCC by measuring the potential differences by initial blocking ENaC with amiloride, then using chloride free solution and isoproterenol to evaluate CFTR function, followed by ATP to evaluate CaCC function. In the other nostril, the same experiment will be repeated as mentioned above, except that after blocking ENaC with amiloride and perfusion with chloride-free solution the CFTR will not be stimulated with isoproterenol, but ATP will be used to maximize the CaCC signal. We will adjust the way of measuring the NPD for aim 2.2 depending of the results in aim 2.1.

TGF-ß and citokines will be measured using Leukosorb, a noninvasive sampling method of the nasal mucosa as previously reported. In addition, we will obtain a small amount of nasal epithelial cells to measure TGF-ß by qPCR.

Study Visits:

V1 (Screening Visit): This will be a single visit for the purpose of determining eligibility, obtaining informed consent, and recording the necessary data will include:

- Assessment of general health status and physical examination (incl. vital signs)
- Urine pregnancy test if indicated (female, child bearing age)
- Spirometry pre- and post-bronchodilators, DL_{co}, lung volumes
- Pulse oximetry
- Review of laboratory values, or if not available: venous blood sampling to assess for renal and liver abnormalities (then the measurements will be done within a week in an additional visit), CRP
- If inclusion criteria fulfilled and no exclusion criteria found:
 - Enrollment

- Completion of respiratory questionnaires (COPD only)
- Six minute walk test (COPD only)
- BODE index calculation

V2 (week 4): This visit (and the two following ones) will only done for the groups not treated with any ARBs. This visit will occur 4 weeks (\pm 4 days) after V1.

- We will again review laboratory values (CMP, CRP), repeat urine pregnancy test if indicated (female, child bearing age).
- The following procedures will be executed:
 - Completion of respiratory questionnaires (COPD only)
 - Six minute walk test (COPD only)
 - BODE index calculation
 - NPD measurement followed by nasal fluid recovered by Leukosorb filter paper and nasal cell collection for TGF-ß

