 - Subjects will be provided with a 4-week supply of 50 mg losartan for daily use (first dose given in clinic; observation with blood pressure monitoring for 2 hours).

V3 (week 5 ± 4 days):

Telephone visit to follow up on symptoms and tolerability of medication.

V4 (week 8 ± 4 days):

- The following procedures will be executed:
 - Monitor for adverse events.
 - Completion of respiratory questionnaires (COPD only)
 - Six minute walk test (COPD only)
 - Venous blood sampling to assess for renal and liver abnormalities and CMP, CRP
 - Urine pregnancy test (if applicable)
 - BODE index calculation
 - Nasal fluid recovered by Leukosorb filter paper and nasal cell collection for TGF-ß
 - Subjects will be provided with a 4-week supply of 50 mg losartan for twice daily use (100 mg)

V5 (week 9 ± 4 days):

Telephone visit to follow up on symptoms and tolerability of medication.

V6 (week 12 ± 4 days) or Early Termination Visit:

- We will draw laboratory (CMP, CRP). Repeat pregnancy test if indicated (female, child bearing age).
- The following procedures will be executed:
 - Monitor for adverse events.
 - Completion of respiratory questionnaires(COPD only)
 - Venous blood sampling to assess for renal and liver abnormalities and CMP, CRP
 - Urine pregnancy test (if applicable)
 - Six minute walk test (COPD only)

- BODE index calculation
- NPD measurement followed by nasal fluid recovered by Leukosorb filter paper and nasal cell collection for TGF-ß

Unscheduled visit (up to 2 visits) will apply if there is a need to repeat study procedures.

Subjects are allowed to be re-screened one time as per PI discretion.

Specimen Banking

Not applicable.

Data Management

Data collected will include demographics, clinical symptoms, health-related quality of life, and pulmonary function test data. Samples to be collected include NPD measurement followed by nasal fluid and cell collection for TGF-ß. We will obtain blood for safety reasons (liver and renal function) and for evaluation of an inflammatory marker. No personal identifiers will be collected and each patient's data will be coded.

Safety Reporting

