COPD is more common among men than women, although the prevalence is increasing in women. COPD is rare among African-Americans. Less information is available about Hispanics, which are a heterogeneous group. The planned accrual of minority groups reflects the prevalence of COPD in our region in South Florida.

Setting

The Human Research Laboratory, Division of Pulmonary, Allergy, Critical Care and Sleep Medicine, is located on the 6th floor of the Doctor's Office West Building at the University of Miami on the Medical School Campus. It has 2,200 square feet of space for evaluation of patients for pulmonary research. This space is equipped with spirometers, a nSpire[®] HDpft plethysmograph including DLco measurement, , blood pressure machines, pulseoximeters, 12-lead ECG machine, ACLS equipment and setup for 6-minute walk tests, including O₂ tanks, an HP 78352A monitor for heart rate and ECG monitoring (3 lead ECG cables). Other equipment includes a DeVilbiss nebulizer, Ultrasonic nebulizer and - 20°C freezer.

We have the ability to draw blood, prepare specimens for laboratory analysis. Our staff is BLS, GCP, OSHA and IATA certified and follows UN 1845 and 3373 regulation for the guidelines of shipping biological materials. Physicians are BLS and ACLS certified. We have a fully functional nasal potential difference (NPD) measurement unit (use certified by Cystic Fibrosis Foundation Therapeutic Development Network: CFF TDN). [name] has an office within this setting.

Recruitment Methods

Forty subjects will be enrolled from two outpatient clinics run by members of the Division of Pulmonary, Allergy, Critical Care and Sleep Medicine, Department of Medicine, at the University of Miami Miller School of Medicine considering 20% of screening failure to enroll 30 patients on the treatment phases. Collectively, ~400 patients with COPD are seen at the two sites annually. Smokers without COPD and lung-healthy lifetime non-smokers will be recruited from the pre-operative clinics at the University of Miami Hospitals and Clinics.

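### The open-label, fixed-sequence protocol states no masking of NPD scoring to visit or dose, so a systematic scoring difference would be counted as a losartan effect in the within-person comparison

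*Combined protocol and SAP*

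**What the plan says.** The Background section sets the design: "This is a proof of concept, open label protocol". The Objectives test the hypothesis "by assessing nasal potential difference (NPD), a surrogate for potential differences in epithelia of the lower airways", with measurements in the untreated state and then "repeated while giving 50 mg and subsequently 100 mg losartan for 4 weeks each". The order is the same for everyone, so knowing the visit means knowing the dose. Under Treatment arms the comparison is within person: "We will compare treatments using baseline measurements of each individual as his/her own control".

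On how NPD is obtained, Study Procedures says that it "will be performed according to standard procedures" and lists the perfusion steps, with the response to ATP as the measure of CaCC function. It does not say who scores a tracing, by what rule, or whether the scorer knows the visit.

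Three other statements come near the question without settling it:
- Setting describes the NPD unit as "use certified by Cystic Fibrosis Foundation Therapeutic Development Network".
- Data Management says "No personal identifiers will be collected and each patient's data will be coded".
- Study Drug says that losartan is "given to the subjects by the PI or study coordinators".

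Assessment of efficacy is entered as not applicable. Statistical analysis names regression for differences between groups and doses.

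**The concern.** The Background section gives the expected direction: the team's preliminary data suggest that losartan partly restores BK channel function. If the person who scores the tracings knows which are baseline and which are on drug, that expectation can shift the scores.

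In a trial with a masked concurrent control, such a shift would largely cancel between arms. Here the dose effect is read from each subject's change from baseline, so the shift goes directly into the estimate. The planned analysis has no term that could separate it from a drug effect. What is at stake is the study's central result, the change in NPD from untreated to 50 mg and 100 mg.

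**Working it through.** **1. Is masking stated anywhere?** The places where it could appear, taken in turn:
- NPD measurement (Study Procedures): standard procedures and perfusion steps; nothing on masked, coded, independent or central scoring.
- Study Visits and the schedule in Appendix I: when NPD is done, not how it is scored.
- Setting: certification of the unit's use, which says nothing about what the scorer knows.
- Data Management: coding is mentioned together with personal identifiers. It protects identity and is not said to hide visit or dose.
- Statistical analysis, and Quality Control & Quality Assurance: silent.

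So masked scoring is not stated.

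**2. Where does a scoring shift go?** For one subject, let the true change from baseline be d and let on-treatment tracings be scored higher by s.
- Within-person contrast: observed change = d + s. The whole of s is counted as drug effect.
- Between-group comparison of change: (d₁ + s) − (d₂ + s) = d₁ − d₂. A shift common to both groups cancels.

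The exposure is therefore the within-person dose contrast.

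**3. How much could it matter?** The documents give no NPD standard deviation, effect size, alpha, sidedness or power, so there is no planned power figure to reproduce. What follows is an illustration on stated assumptions.

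Assumptions: paired t-test, two-sided alpha 0.05, no true losartan effect, and a scoring shift of b standard deviations of the paired change.

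Inputs for n: 10 and 20 are the group sizes under Study Population; 30 is the number for the treatment phases under Recruitment Methods. These do not agree with one another (10 + 20 + 20 = 50), which is a separate matter and the reason for showing a range.

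Formula: with noncentrality λ = b√n and critical value c from the t distribution on n − 1 degrees of freedom, the false-positive rate is P(T > c) + P(T < −c), where T is noncentral t with n − 1 degrees of freedom and noncentrality λ.

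Example: n = 20, b = 0.5 gives λ = 0.5 × √20 = 2.236, c = 2.093, rate = 0.5645.

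| n | b = 0 | b = 0.1 | b = 0.2 | b = 0.3 | b = 0.5 |
|---|---|---|---|---|---|
| 10 | 5% | 6% | 9% | 14% | 29% |
| 20 | 5% | 7% | 14% | 25% | 56% |
| 30 | 5% | 8% | 19% | 36% | 75% |

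For a fixed shift the rate rises with n, because a larger sample estimates the bias more precisely and does not average it away.

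**4. Which tracings are involved?** The V4 procedure list under Study Visits contains no NPD measurement. Appendix I marks NPD at Visit 4, and the Objectives call for NPD during the 50 mg period. V2 and V6 carry NPD in both places. The baseline to 100 mg contrast is thus exposed in any case; the 50 mg contrast depends on how V4 is settled.

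**The case against.** **The documents are silent, and silence is not proof that scoring is unmasked.** This stands. The standard procedures may contain scoring rules or masked reading that cannot be seen here. A reader might infer from the Study Drug section that the staff who hand out losartan also score the tracings. The documents do not say so: they name who gives the drug and leave the scorer unnamed. The supportable statement is that masking is not stated.

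**The magnitude is assumed.** This stands too. NPD is an instrument-recorded voltage, and nothing shows how much judgement enters its scoring. Any bias fed into a t-test raises the false-positive rate, and the plan names regression, not a paired t-test. The table shows sensitivity to a shift; it does not estimate this trial's error rate.

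**Coded scoring would not prevent the bias.** A reader might infer that coding by the same staff closes the gap entirely. It does not. NPD is a live procedure with sequential perfusions, and operator expectation during recording is untouched. Someone who recorded a tracing may recognise it later. Time, learning and regression to the mean remain confounded with dose.

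**Delayed scoring could cost data.** The protocol allows up to two unscheduled visits to repeat procedures, and an untreated baseline cannot be repeated once losartan has started at V2. The NPD section also says that the method for one aim will be adjusted on the results of another; the aims are not defined in this document, but late readings could affect that. The first point calls for a technical check at the visit; the second should be confirmed before adoption.

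**An open-label, own-control design is a declared choice for a proof-of-concept study.** Accepted. But open-label treatment does not require open-label scoring of the outcome that tests the hypothesis.

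**Conclusion.** The point holds in a limited form. The study is open label, the dose order is fixed, the main comparison is within person, and no section states that NPD scoring is masked to visit or dose. A systematic difference in scoring between baseline and on-treatment tracings would therefore be counted as a losartan effect in that comparison. A shift common to all groups would largely cancel in between-group comparisons of change.

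The size cannot be derived from the documents. Under the assumptions in the working, a shift of 0.1 to 0.5 SD of the paired change moves the false-positive rate from 5% to 6–29% (n=10), 7–56% (n=20) or 8–75% (n=30). The documents show neither that a shift will occur nor that scoring is in fact unmasked. The change is worth making because it is cheap and no treatment decision in the protocol depends on an NPD result.

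**What to change.** First reconcile the V4 procedure list with Appendix I and the Objectives on whether NPD is measured at V4.

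Then add to the NPD measurement section:
- Each tracing is saved under a random code that carries no subject, date, visit or dose.
- At the visit the operator makes only a technical-quality check, so that a failed tracing can be repeated; at V2 this check is completed before the first dose.
- After the subject's last visit, existing staff score the coded tracings in random order by a prespecified rule. Where possible the scorer is someone who did not record that tracing.
- Values are locked before the code is opened.

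This adds no arm, visit, procedure or extra staff. The cost is that readings become available later, plus a little work to assign and hold the codes. It assumes that tracings can be stored and scored afterwards, which the documents do not say. If the laboratory's standard procedures already mask scoring, a sentence stating this and the scoring rule would be enough.

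The report should still acknowledge that operator expectation during live measurement, and time effects confounded with dose, remain.

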20 active smokers not treated with ARBs **without** evidence of airflow obstruction by PFT and **normal** DLco but **with** the clinical diagnosis of chronic bronchitis.

Group III, lung healthy, life-time non-smoker:

20 never smokers not treated with ARBs **without** evidence of airflow obstruction by PFT, a **normal** DLco **and no** evidence of the clinical diagnosis of chronic bronchitis

Groups will be appropriately balanced considering COPD stage, smoking status, lung function and age.

Inclusion and Exclusion Criteria

Inclusion criteria

- Age between 35 and 75 years old
- ex-smokers (>10 pack-years of cigarette smoking) not treated with ARBs and with evidence of fixed airflow obstruction by pulmonary function testing (PFT), decreased DLco and with the clinical diagnosis of chronic bronchitis. Or

active smokers (>10 pack-years of cigarette smoking) not treated with ARBs **without** evidence of airflow obstruction by PFT and **normal** DLco but **with** the clinical diagnosis of chronic bronchitis.

Or

never smokers not treated with ARBs **without** evidence of airflow obstruction by PFT, a **normal** DLco **and no** evidence of the clinical diagnosis of chronic bronchitis

• Ability to understand and willingness to sign consent documents

Exclusion criteria:

- Current therapy with ACE inhibitor, intolerance to ARB
- Women of child bearing potential
- Regular use of NSAIDs or potassium supplementation, treatment with aliskiren, anticoagulation
- COPD exacerbation requiring treatment within 6 weeks
- Oral corticosteroid use within 6 weeks
- Significant hypoxemia (oxygen saturation <90% on room air), chronic respiratory failure by history (pCO₂ > 45 mmHg) and forced expiratory volume in 1 second (FEV₁) below 40%, clinical evidence of cor pulmonale

- Untreated arterial hypertension (systolic blood pressure >140 mm Hg, diastolic blood pressure > 90 mm Hg)
- Blood pressure less than 100 mm Hg systolic or 70 mm Hg diastolic at Screening visit and Visit 2.
- Cardiac, renal, hepatic (LFTs > 3x normal upper limit), neurological, psychiatric, endocrine or neoplastic diseases that are judged to interfere with participation in study
- History of renal artery stenosis
- Concomitant airway disorders other than COPD and chronic bronchitis, such as bronchiectasis and asthma (history and reversible airflow obstruction by ATS criteria)
- History of pulmonary malignancies, and any other malignancies in the last 5 years
- History of thoracic surgery.

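### The groups cannot be balanced on smoking status, lung function or COPD stage, because these define them; a Group I versus Group II difference cannot be attributed to COPD rather than current smoking

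*Combined protocol and SAP*

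**What the plan says.** The Study Population section sets up three groups and then says "Groups will be appropriately balanced considering COPD stage, smoking status, lung function and age".

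- Group I, labelled COPD: "10 ex-smokers not treated with ARBs", with fixed obstruction, reduced DLco and chronic bronchitis.
- The next group is labelled "Group II, non-COPD": "20 active smokers not treated with ARBs", without obstruction, with normal DLco and with chronic bronchitis.
- Group III: "20 never smokers not treated with ARBs", with normal lung function and no chronic bronchitis.

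The Inclusion criteria repeat these definitions and add a smoking threshold to Groups I and II; for Group II it reads "active smokers (>10 pack-years of cigarette smoking) not treated with ARBs". The purpose sentence at the end of Background refers to "cigarette smoke-induced lung injury in smokers, ex-smokers with and without COPD". Under Study Procedures, "Urine cotinine levels will be measured at the time of study visits to assess smoking status (active or not").

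The Statistical analysis section plans regression for differences between groups and doses, and a multivariate comparison of test results between groups. It names no covariates. Objectives and Treatment arms plan a separate comparison in which each subject serves as his or her own control. No matching or stratification procedure is described anywhere.

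**The concern.** The balance sentence promises a property that the design cannot have. Someone relying on it could take Group I versus Group II as a comparison of COPD with non-COPD, made at similar smoking status and lung function. Smoking status and lung function differ between these two groups by definition.

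The consequence matters here because, by the Background, smoke exposure and COPD act on the same pathway: TGF-ß signalling is raised both in active smokers and in ex-smokers with COPD. A difference between Groups I and II could come from either factor, and two real effects could cancel.

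**Working it through.** The protocol gives no figure to reproduce for this point, and no alpha, power or variance is needed. The question is whether a COPD effect can be estimated from the group definitions.

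**Inputs (Study Population, Inclusion criteria)**

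| | n | COPD (C) | Active smoker (S) | Ever-smoker (E) | Chronic bronchitis (B) |
|---|---|---|---|---|---|
| Group I | 10 | 1 | 0 | 1 | 1 |
| Group II | 20 | 0 | 1 | 1 | 1 |
| Group III | 20 | 0 | 0 | 0 | 0 |

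**Step 1. What can be balanced.** Smoking history takes a different value in each group. If smoking status means only active or not, as in the cotinine paragraph, Groups I and III agree but Group II still differs from both. Lung function is abnormal by definition in Group I and normal in the other two, so it can be balanced only within the normal range, between Groups II and III. COPD stage has no value outside Group I. Age is the only listed factor that can be balanced across all three.

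**Step 2. Groups I and II.** The four COPD-by-active-smoking cells are: COPD and active 0; COPD and not active 10; no COPD and active 20; neither 0. With n = 30:

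- mean C = 10/30 = 1/3; mean S = 20/30 = 2/3; mean of C×S = 0
- covariance = 0 - (1/3)(2/3) = -2/9
- var C = var S = (1/3)(2/3) = 2/9
- correlation = (-2/9)/(2/9) = -1

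Since C + S = 1 for every subject, the columns intercept, C and S have rank 2 for 3 parameters. Under mean = a + bC·C + bS·S, Group I minus Group II = (a + bC) - (a + bS) = bC - bS. Only this difference can be estimated. As an illustration with assumed effects in SD units: bC = bS = 0.5 gives 0; bC = 0.5, bS = 0 gives 0.5; bC = 0, bS = 0.5 gives -0.5.

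**Step 3. Adding Group III.** The columns intercept, C and S now have rank 3 of 3, and the COPD coefficient equals mean(I) - mean(III). That is a COPD effect only if ever-smoking and chronic bronchitis have no effect. Adding either E or B gives rank 3 for 4 parameters, and COPD is again not estimable: with both, Group I minus Group III = bC + bE + bB.

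**Step 4. Losartan change.** Each subject's change from baseline removes whatever is constant within that subject, so the own-control contrast does not depend on separating C from S. Comparing mean change between Groups I and II puts change in place of the outcome in Step 2 and has the same aliasing.

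**Step 5. Two linked contradictions.**

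- NPD at V4: the V4 list under Study Visits has nasal fluid and cell collection but no NPD. Appendix I marks NPD at that visit, and Objectives call for NPD during the 50 mg period.
- Number treated: Recruitment Methods give 30 in the treatment phases. The groups sum to 10 + 20 + 20 = 50. Study Visits opens V2 and later visits to groups not on ARBs, which describes all three. Thirty fits Groups I and II (10 + 20) and equally Groups I and III (10 + 20).

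**The case against.** The strongest reply is that no stated aim needs the COPD contrast. The hypothesis concerns losartan within individuals, the purpose sentence lists populations and does not announce a comparison, and the Statistical analysis section attributes no group difference to COPD. This stands and sets the weight of the point. It does not remove it: the group comparison is planned, the groups carry COPD and non-COPD labels, and the balance sentence is still one the design cannot satisfy.

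The sentence might instead mean a spread of stages within Group I, but it speaks of groups and gives no within-group scheme. It might also be left over from a design with ARB-treated subjects, since Study Visits and Appendix I still distinguish subjects not on ARBs. If so, deleting it is the right remedy.

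Some stronger readings are tempting but not supported:

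- A reader might infer that COPD also coincides with recruitment source. Recruitment Methods take forty subjects from two outpatient clinics and then say that smokers without COPD and never-smokers come from pre-operative clinics. That is too ambiguous to state the overlap as fact.
- A reader might infer that the enrolment arithmetic is wrong because 40 × 0.80 = 32. But 30/0.80 = 37.5, and 40 is a reasonable rounding up. The substantive question is 30 against 50.
- A reader might infer that V2 to V6 should be the main contrast. The documents do not rank the doses. V6 also serves as the early termination visit, and its timing conflicts: week 12 with V2 at week 4 in Study Visits, against 12 weeks after V2 in Appendix I.

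**Conclusion.** The point holds for the group conclusions only. The promised balance is impossible for smoking status, for COPD stage, and for lung function between Group I and the others. Within Groups I and II, COPD and active smoking are perfectly aliased (correlation -1, rank 2 of 3), and adding Group III does not separate COPD once ever-smoking or chronic bronchitis is allowed an effect. These results follow from the group definitions alone and do not depend on the group sizes. Recording cotinine as active or not cannot help, because it reproduces the split between Groups I and II.

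A reader might infer that the trial cannot answer its main question. The documents do not support that: the within-subject losartan comparison in Objectives and Treatment arms does not rely on the groups being comparable. The sentence should be corrected, but the design need not be rejected.

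**What to change.** 1. In Study Population, delete the balance sentence or replace it with wording such as:

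> Groups will be balanced on age as far as recruitment allows. Smoking history, COPD and lung function differ between groups by design. Group contrasts describe the enrolled groups and do not separate COPD from current smoking.

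2. Reconcile NPD at V4 across Objectives, the V4 list and Appendix I. If the V4 list is followed as written, the 50 mg NPD comparison is lost.

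3. Reconcile the 30 in Recruitment Methods with the 50 in Study Population and the access rule at V2, and state which groups are treated.

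Item 1 is a change of wording with the same subjects and visits. Its cost is a narrower stated conclusion for group contrasts. Items 2 and 3 ask the sponsor to say which existing text applies. Separating COPD from current smoking would need a further group, for example ex-smokers with chronic bronchitis but no COPD. Added to Groups I and II, it raises the rank to 3 of 3 if effects are additive. That would be a design change, and it is not needed for the own-control question.
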